5.6 Follow-up Assessments and Study Completion

After discontinuation of study drug treatment, participants will continue to be evaluated for safety and survival data. The following visits will be performed:

28 Day Safety Visit: All participants will have a follow-up visit scheduled 28 days (± 7 days) after the last dose of study treatment to follow-up for AEs and SAEs. AEs and SAEs that are still ongoing at the time of discontinuation and considered as related to study treatment will continue to be followed weekly until resolution, stabilization of condition, or end of study.

Treatment Follow-up Period: Any participant who is discontinued from study treatment for any reason other than disease progression will continue to have tumor assessments every 12 weeks until progression, death or until a new anti-neoplastic therapy is initiated. The investigator, or his/her designee, will continue to collect information until the first initiation of additional anti-neoplastic therapies for each discontinued participant until one year following last participant last visit.

All participants who have progressed during study treatment or during the Treatment Follow-up Period will be followed every 12 weeks for survival up to 1 year after the last participant is discontinued from the study.

5.7 Treatment Holidays

In general, a 48 hour window is allowed for study drug treatments, unless other restrictions are stated.

6. EXPECTED TOXICITIES AND DOSING DELAYS/DOSE MODIFICATIONS

6.1 Anticipated Toxicities

The preclinical safety evaluation showed that the toxicity profile of AUY922 is dominated by cytotoxic and inflammatory reactions in the intestine, bone marrow and lymphoid tissue, as well as a moderate risk of local irritation at the injection site. The observed changes were reversible in the animal experiments. Nevertheless, there is a probability that participants may experience diarrhea following treatment with AUY922. Safety pharmacology studies revealed no effects on CNS or respiratory functions.

Based on *in vitro* and *in vivo* data, a potential for cardiovascular toxicity, such as QTc prolongation or proarrhythmia could not be completely excluded. *In vitro* cardiac safety studies demonstrated a pre-clinical signal for QT prolongation, however, no effects on QT or QTc were observed in the GLP dog and monkey telemetry studies *in vivo*. Due to potential cardiac toxicity, participants in ongoing studies are undergoing careful cardiac monitoring.

No potential for genotoxicity (*in vitro* and *in vivo*) or phototoxicity (*in vitro*) was found in the preclinical safety studies conducted so far.

In conclusion, main target organs for AUY922 are the intestine, bone marrow and lymphoid tissue. There may be a risk of QTc prolongation, and of a local irritative effect. These safety parameters can be monitored in the clinic using an intensive ECG and vital signs monitoring schedule. Detailed instructions for the observation and treatment of diarrhea are also provided in this study protocol.

6.2 AUY922 Dose Modifications / Delays

Toxicity will be assessed using the NCI-CTC for Adverse Events, version 4.02 (CTCAE v4.02)

For participants who are unable to tolerate the protocol-specified dosing schedule, dose adjustments are permitted in order to keep the participant on study drug (Tables 6-1). If the participant experiences unacceptable toxicities, treatment with the study drug must be suspended until the toxicities return to \leq CTCAE grade 1. Special instructions are provided for QTcF, gastrointestinal, and ocular toxicities. The criteria for interruption and re-initiation of AUY922 treatment are outlined in Table 6-1.

CONFIDENTIAL

This document is confidential. Do not disclose or use except as authorized.

Page 24 of 69

Table 6-1 Criteria for interruption, dose reduction and re-initiation of AUY922 study treatment

Recommended dose modifications for AUY922	
Worst toxicity	During a cycle of therapy
CTCAE grade* (value)	
No toxicity	Maintain dose level
Hematologic	
Neutropenia (ANC)	
Grade 1 (ANC < LLN - 1500/mm ³)	Maintain dose level
Grade 2 (ANC < 1500 - 1000/mm ³)	Maintain dose level
Grade 3 (ANC < 1000 - 500/mm ³)	Omit dose until resolved to ≤ grade 1 If resolved in ≤ 7 days, maintain dose level If resolved in > 7 days, then dose reduce to 54 mg/m ²
Grade 4 (ANC < 500/mm ³)	Omit dose until resolved to ≤ grade 1, then dose reduce to 54 mg/m ²
Febrile neutropenia (ANC < 1.0 x 10 ⁹ /L, fever ≥ 38.5°C)	Omit dose until resolved, then dose reduce to 54 mg/m ²
Thrombocytopenia	
Grade 1 (PLT < LLN - 75,000/mm ³)	Maintain dose level
Grade 2 (PLT < 75,000 - 50,000/mm ³)	Omit dose until resolved to ≤ grade 1 If resolved in ≤ 7 days, maintain dose level If resolved in > 7 days, then dose reduce to 54 mg/m ²
Grade 3 (PLT < 50,000 - 25,000/mm ³)	Omit dose until resolved to ≤ grade 1 If resolved in ≤ 7 days, maintain dose level If resolved in > 7 days, then dose reduce to 54 mg/m ²
Grade 4 (PLT < 25,000/mm ³)	Omit dose until resolved to ≤ grade 1, then dose reduce to 54 mg/m ²
Renal	
Serum creatinine	

Recommended dose modifications for AUY922	
During a cycle of therapy	
Worst toxicity	
CTCAE grade* (value)	
Grade 1 (> ULN - 1.5 x ULN; >1 - 1.5x baseline)	Maintain dose level
Grade 2 (> 1.5 - 3.0 x ULN; >1.5 - 3.0x baseline)	Omit dose until resolved to ≤ grade 1, then dose reduce to 54 mg/m ²
Grade 3 (> 3.0 - 6.0 x ULN; >3x baseline)	Omit dose and discontinue patient from study
Grade 4 (> 6.0 x ULN)	Omit dose and discontinue patient from study
Hepatic	
Bilirubin	
Grade 1 (> ULN - 1.5 x ULN)	Maintain dose level
Grade 2 (> 1.5 - 3.0 x ULN)	Omit dose until resolved to ≤ grade 1, dose reduce to 54 mg/m ²
Grade 3 (> 3.0 - 10.0 x ULN)	Omit dose until resolved to ≤ grade 1, dose reduce to 54 mg/m ²
Grade 4 (> 10.0 x ULN)	Omit dose and discontinue patient from study
AST or ALT	
Grade 1 (> ULN - 3.0 x ULN)	Maintain dose level
Grade 2 (> 3.0 - 5.0 x ULN)	Maintain dose level
Grade 3 (> 5.0 - 20.0 x ULN)	Omit dose until resolved to ≤ grade 1 (or ≤ grade 2 if liver metastases present), then if resolved in ≤ 7 days, maintain dose level
Grade 4 (> 20.0 x ULN)	If resolved in > 7 days, then dose reduce to 54 mg/m ² Omit dose until resolved to ≤ grade 1, then dose reduce to 54 mg/m ²
Cardiac	
Cardiac - prolonged QTcF interval	
During cycle 1:	
Absolute QTcF < 480msec	Maintain dose level. ECG monitoring assessments should be performed as per visit schedule

CONFIDENTIAL

This document is confidential. Do not disclose or use except as authorized.
Page 26 of 69

Recommended dose modifications for AUY922	
During a cycle of therapy	
Worst toxicity CTCAE grade* (value)	
Absolute QTcF ≥ 480 msec and < 500 msec	
Maintain dose level. ECG monitoring assessments should be performed for 2 additional cycles at the same frequency as in cycle 1. After the second additional cycle, ECGs for subsequent cycles will be performed as follows:
 
If ECG in the additional cycles show no absolute QTcF ≥ 480msec then for subsequent cycles ECG monitoring will be performed as per visit schedule.
 
If ECG is still abnormal (absolute QTcF ≥ 480msec and < 500msec) then ECG monitoring must continue at the same frequency as in cycle 1 for all subsequent cycles.
 
Omit dose administration. Monitor patient with hourly ECGs until the QTcF has returned to ≤ 450msec. Perform further monitoring as clinically indicated. Exclude other causes of QTcF prolongation such as hypokalemia, hypomagnesemia and blood oxygenation status. Participants who develop hypokalemia or hypomagnesemia during the study should receive electrolyte replacement as soon as possible and should not receive further AUY922 dosing until the respective electrolytes are documented to be within normal limits.
 
Once the QTcF prolongation has resolved, participants may be re-treated at 54 mg/m^2 at the investigator's discretion. ECG monitoring must continue throughout the treatment period as follows:
 
ECG monitoring assessments should be performed for 2 additional cycles at the same frequency as in cycle 1. If the ECGs obtained in the first and second additional cycles after dose reduction are without any QTc prolongation, then ECG monitoring in subsequent cycles will continue as per the visit schedule.
 
If the participants had an absolute QTcF ≥ 480msec and < 500msec, then ECG monitoring at the same frequency as in cycle 1 will be continued for all subsequent cycles.
 
Participants who experience absolute QTcF ≥ 500msec after dose reduction to 54 mg/m^2 will be discontinued from study.
 
NB: If Torsades de Points is observed, participant should be discontinued from the study.
 
Whenever QTcF ≥ 500msec is observed, a plasma sample for determination of AUY922 concentration should be obtained with the time of sample collection noted.

Cardiac general	
Grade 1 or 2	Maintain dose level
Grade 3	Omit dose until resolved to \leq grade 1, then dose reduce to 54 mg/m^2
Grade 4	Omit dose and discontinue participant from study

CONFIDENTIAL

Recommended dose modifications for AUY922	
During a cycle of therapy	
Worst toxicity	
CTCAE grade* (value)	
Diarrhea	
Grade 1	Maintain dose level
Grade 2 (see Section 6.3.1 for recommended treatment algorithm)	Omit dose until resolved to grade 1 or baseline If resolved in ≤ 7 days, maintain dose level If resolved in > 7 days, dose reduce to 54 mg/m ²
Grade 3 (see Section 6.3.1 for recommended treatment algorithm)	Omit dose until resolved to grade 1 or baseline, then dose reduce to 54 mg/m ²
Grade 4 (see Section 6.3.1 for recommended treatment algorithm)	Omit dose until resolved to grade 1 or baseline, then dose reduce to 54 mg/m ² If grade 4 toxicity lasts < 24 hours, then dose reduce to 54 mg/m ² . If grade 4 toxicity recurs, discontinue treatment. In the event grade 4 toxicity lasts > 24 hours despite optimal use of anti-diarrheal, discontinue treatment.
Visual symptoms or signs	
Grade 1	Maintain dose level
Grade 2	Omit dose administration until resolved to ≤ grade 1 (or baseline), then continue treatment with AUY922 at the current dose level If visual symptoms ≥ Grade 2 recur upon re-exposure to AUY922, omit dose until resolution to ≤ Grade 1, then dose reduce to 54 mg/m ² and maintain this dose level. If visual symptoms ≥ Grade 2 recur at a dose of 54 mg/m ² , then the participant should be discontinued from the study.
Grade 3	Omit dose administration until resolved to ≤ grade 1 (or baseline), then dose reduce to 54 mg/m ²
Grade 4	Omit dose administration and discontinue patient from study
Other adverse events**	
Grade 1 or 2	Maintain dose level
Grade 3	Omit dose until resolved to ≤ grade 1, then dose reduce to 54 mg/m ²
Grade 4	Omit dose and discontinue participant from study

CONFIDENTIAL

This document is confidential. Do not disclose or use except as authorized.
Page 28 of 69

Recommended dose modifications for AUY922	
Worst toxicity	During a cycle of therapy
CTCAE grade* (value)	
All dose modifications should be based on the worst preceding toxicity.	
Each participant is allowed only one dose reduction. Participants must discontinue treatment with AUY922 if, after treatment is resumed at a lower dose, the same toxicity recurs with the same or worse severity. Similarly, participants who have already required prior dose reduction to 54 mg/m ² for a given toxicity must be discontinued from treatment with AUY922 if a separate toxicity occurs that would otherwise require dose modification.	
If a participant requires a dose interruption of > 28 days from the last dose, then the participant must be discontinued from the study. Participants who discontinue the study for a study related adverse event or an abnormal laboratory value must be followed.	
*Common Toxicity Criteria for Adverse Events (CTCAE Version 4.0).	
**During the administration of AUY922, the infusion should be stopped if the participant experiences CTCAE grade 2 cardiovascular toxicity or any ≥ CTCAE grade 3 toxicity.	

Participants who experience adverse events that require dose reduction will be treated at 54 mg/m² upon resolution of the adverse event.

6.3 Toxicity Management

6.3.1 Diarrheal Precautions

Both preclinical toxicology studies and clinical studies have shown AUY922 to cause gastrointestinal toxicities including diarrhea. In the event diarrhea is observed in participants the below management plan should be followed. This treatment algorithm is based on publications on how to manage diarrhea caused by cytotoxic regimens (Wadler 1998, Kornblau 2000).

First report of diarrhea

Please obtain a history of onset and duration of the diarrhea. This should include the description of number of stools from participants and stool composition (e.g. watery, presence of occult blood or mucus in stool etc.) Fever should be assessed and details should be obtained whether participant is also experiencing abdominal pain, cramps, bloating, distension, nausea, vomiting, dizziness and weakness in order to rule out the risk of sepsis, bowel obstruction or dehydration. Please review participant's medication profile and identify any diarrheogenic agents. Please also ask about participant's dietary profile to identify any diarrhea causing foods. Participants should be checked after starting AUY922 to proactively look for start of diarrhea so that anti-diarrheal treatment can be started as soon as possible to limit severity of the diarrheal toxicity. Call participants at home, if necessary, early during the first 8 weeks of AUY922 treatment start. Instruct the participant to call at the first sign of diarrhea.

Management of diarrhea

Participants should be instructed to stop all lactose-containing products and alcohol consumption after starting AUY922 treatment. Participants should also refrain from using laxatives, bulk fiber and stool softeners. Participants should be encouraged to drink 8 to 10 glasses of clear liquids a day and try to eat frequent small meals. High osmolar food supplements such as Ensure Plus[®] should be avoided.

Participants should be provided with loperamide tablets (or alternative anti-diarrheal agent). It is mandatory that participants are instructed on the use of loperamide in order to manage signs or symptoms of diarrhea at home. All medications that participants take should be recorded. Participants should be instructed to start taking oral loperamide (initial administration of 4 mg, then 2 mg every 4 hours, for a maximum of 16 mg/day) at the first sign of loose stool or symptoms of abdominal pain. Participants should be reminded of the use of loperamide during each clinic visit.

Treatment of Grade 1 and Grade 2 diarrhea

Grade 1 or grade 2 diarrhea will be treated with standard loperamide regimen (initial administration of 4 mg, then 2 mg every 4 hours, for a maximum of 16 mg/day). If diarrhea resolves within the next 24 hours continue instructions listed above for dietary modification and for participants to gradually introduce solid foods to their diet. Once participant has been event free for 12 hours loperamide use may be discontinued.

If diarrhea does not resolve after 24 hours, opium tincture or dihydrocodeine tartare tablets/injections should be added to the loperamide treatment. Participant should also be monitored to rule out dehydration, sepsis and ileus. Also refer to diarrhea work up section and determine if hospitalization is required. Continue to observe participant for response to antidiarrheal treatment.

If diarrhea resolves within 24 hours following opiate treatment, continue instructions listed above for dietary modification and for participant to gradually introduce solid foods to their diet. Once participant has been event free for 12 hours loperamide and opiate treatment use may be discontinued.

If diarrhea does not resolve after 24 hours after 2x24 hours loperamide treatment and opiates then admit participant to hospital and follow instructions below for grade 3 and grade 4 diarrhea until toxicity is resolved.

Treatment of grade 3 and grade 4 diarrhea

Participants experiencing grade 3 and grade 4 diarrhea must be hospitalized. Upon hospitalization participant should be treated with high dose loperamide (initial 4 mg, then 2 mg every 2 hours with addition of opium tincturate or dihydrocodeine tartrate tablets/injections). Participant should receive i.v. fluids and antibiotics if indicated and should be monitored to rule out sepsis, dehydration or ileus. Participant should be followed per diarrhea workup plan. Continue to observe participant for response to anti-diarrheal treatment.

If diarrhea does not resolve despite all these efforts please follow your institutional guidance for such clinical cases.

Diarrhea workup

The following appropriate tests are based on the following publication ([AGA Technical Review on the Evaluation and Management of Chronic Diarrhea 1999](#)).

Spot stool analysis

Collect stool and separate it from urine, use special containers and analyze immediately. If analysis can not be done immediately, freeze samples for later analysis. Examine the collected stool for occult blood and under the microscope examine for fecal leucocytes utilizing Wright staining. The stool should also be examined for C.difficile toxin. Lastly, examine fecal cultures for pathogens such as Shigella and pathogenic E. coli. If it is suspected that the participant might have been in contact with contaminated water, examine fecal cultures for Aeromonas and Pleisiomanas.

Endoscopic examinations

Endoscopic examinations should be only considered **if absolutely necessary**. Participant's bowel is likely to be fragile with evidence of colitis and great care and caution must be exercised in undertaking such an invasive procedure. If endoscopy is undertaken consider gastroscopy to obtain jejunal fluid for assessment of bacterial overgrowth for cultures and biopsy of proximal jejunum to assess extent of inflammatory jejunitis. Also, consider sigmoidoscopy for reassessment of colitis.

6.3.2 Cardiac Safety Management Plan

6.3.2.1 Cardiac function measurements

CONFIDENTIAL

This document is confidential. Do not disclose or use except as authorized.

In telemetry studies in monkeys, no clear effects on the QTc interval have been observed following administration of AUY922. Based upon *in vitro* and *in vivo* data, a potential for cardiovascular toxicity, such as QTcF prolongation or proarrhythmia with AUY922 could not be excluded; therefore, cardiovascular monitoring will be conducted throughout the study.

As part of the screening process, participants will be required to undergo either a MUGA or transthoracic echocardiogram to assess left ventricular ejection fraction (LVEF). Cardiac biomarkers will also be measured at baseline. Participants will also be required to undergo ECG monitoring at baseline. The purpose of this will be to establish an accurate QTc interval. Participants will have a total of 3 ECGs performed at baseline.

Upon initiation of treatment with AUY922, ECGs will be obtained as outlined in Tables 6-1 and 6-2. ECGs will be reviewed by the local investigators or a designee.

6.3.2.2 Cardiac precautions

All participants must have an assessment of serum potassium and magnesium within 72 hours of Day 1 dose administration of every treatment cycle (or more frequently if medically indicated). **Note: Participants who develop hypokalemia or hypomagnesemia during the study should receive electrolyte replacement and should not receive further AUY922 dosing until the respective electrolytes are documented to be within normal limits.** On days 1 and 15 of each cycle, the biochemistry results must be reviewed by the investigator before the participant is treated.

6.3.2.3 Handling algorithm for cardiac changes

If cardiac changes are observed during the above monitoring, please refer to Table 6-1 for dose modifications.

As AUY922 may have an influence on the QTc interval, ECGs will be the key cardiac assessment in this protocol. 12-lead ECG monitoring will be conducted according to the following schedule:

Table 6-2 ECG schedule

Cycle	Day	12-lead ECG	Timing and details
Baseline	Baseline	X	Three 12-lead ECGs.
1	1	X	A 12-lead ECG should be obtained prior to the infusion (timing not specified) and after infusion (within 5 minutes).
	2	X	A 12-lead ECG should be obtained at approximately 24hrs post end of infusion.
	3	X	A 12-lead ECG should be obtained at approximately 48 hrs post end of infusion.

CONFIDENTIAL

This document is confidential. Do not disclose or use except as authorized.

	8	X	A 12-lead ECG should be obtained at pre-infusion (timing is not pre-specified) and after infusion (within 5 minutes).
	15	X	A 12-lead ECG should be obtained at pre-infusion (timing is not pre-specified) and after infusion (within 5 minutes).
All subsequent cycles	1, 8, 15	X	A 12-lead ECG should be obtained at pre-infusion (timing is not pre-specified) and after infusion (within 5 minutes).

6.3.3 Ocular Safety Management Plan

Weekly administration of AUY922 may cause visual symptoms. The visual symptom descriptions from ongoing phase 1 studies have included slow dark-light adaptation or photophobia, blurred vision, floaters and flashes in peripheral vision, dark or black spots, darkening of vision, decreased peripheral vision, color vision disturbances, and dry eye syndrome. The visual symptoms were mostly reported the day after the second or third infusion and typically resolved within a week or two weeks post dose. All visual symptoms were reversible; in some patients the events resolved with omission of a dose or after discontinuation of AUY922 treatment.

Standard ophthalmologic assessments will be required at baseline and follow-up exams will be conducted at the time when visual symptom(s) are reported (if any), at Cycle 3 Day 1 (± 2 days) if no visual symptom(s) are reported, and at study discontinuation.

The following standard ophthalmologic assessments are required:

1. Visual acuity test
2. Intraocular pressure test
3. Slit-lamp test
4. Dilated fundus test
5. Color-vision (Ishihara-plate) test

Additional assessments or tests may be conducted as clinically indicated. Ophthalmologic assessments such as electro-retinograms (ERG) may be conducted, if feasible, at the discretion of the site.

Visual symptoms will be graded using NCI CTCAE 4.02. However, for the acuity test (Snellen charts) the following grading should be applied.

Table 6-3 Visual AE grading for AUY922 using Snellen charts

Toxicity	Grade 1	Grade 2	Grade 3	Grade 4
Decreased Acuity	Decrease of 1 line or less of visual acuity from baseline in either eye despite visual symptoms	Decrease of 2-3 lines of visual acuity from baseline in either eye	Decrease of 4 or more lines of visual acuity from baseline in either eye	20/200 or below

Note: Refers to the visual acuity when a participant wears his or her best eyeglasses. The acuity scores pertain to the better eye.

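### Table 6-3 does not settle which eye sets the visual acuity grade, so an unequal loss can lead to different dosing actions under Table 6-1

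*Combined protocol and SAP*

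**What the plan says.** Section 6.3.3 has visual symptoms graded by CTCAE 4.02 and makes an exception for acuity: "However, for the acuity test (Snellen charts) the following grading should be applied". The table that follows is Table 6-3. Its grade 2 cell reads "Decrease of 2-3 lines of visual acuity from baseline in either eye" and its grade 3 cell reads "Decrease of 4 or more lines of visual acuity from baseline in either eye". Grade 1, a loss of at most one line, uses the same either-eye wording. Grade 4 is an absolute level, 20/200 or below, and names no eye.

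The note under the table has two sentences. The first, "Refers to the visual acuity when a participant wears his or her best eyeglasses", applies naturally to every column. The second is "The acuity scores pertain to the better eye", and it carries no grade limit either.

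The grade feeds the visual symptoms or signs row of Table 6-1 (Section 6.2):

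- Grade 1: the dose is maintained.
- Grade 2: dosing is omitted until the event is back to grade 1 or baseline, "then continue treatment with AUY922 at the current dose level". Reduction to 54 mg/m² comes only if grade 2 or worse symptoms "recur upon re-exposure to AUY922, omit dose until resolution to" grade 1 or lower. A further recurrence at 54 mg/m² ends participation.
- Grade 3: dosing is omitted until recovery, then reduced to 54 mg/m².
- Grade 4: the participant is discontinued.

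**The concern.** The cells and the note give two rules for the same examination. Under the cells, the eye that has lost more lines sets the grade. Under the note, the better eye does. When the two eyes have changed by different amounts, the rules can give different grades, and Table 6-1 attaches different actions to those grades. Two investigators who each follow the printed text could therefore treat the same Snellen result differently. Following the note can keep a participant with a marked loss in one eye on full dose.

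This matters for this drug because visual toxicity is a recognised effect. Section 2.3.3.1 reports grade 3 visual symptoms as dose-limiting in two patients at 70 mg/m², the dose used here.

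**Working it through.** The plan states no figure on this point, so there is none to reproduce. The check applies both rules to the same pair of eyes and reads off the action.

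**Inputs.** Loss bands come from Table 6-3: 0-1 lines (grade 1 at most), 2-3 lines (grade 2), 4 or more lines (grade 3). Actions come from the visual row of Table 6-1. The starting dose is 70 mg/m² and the reduced dose is 54 mg/m².

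**Assumptions.** Both eyes have equal baseline acuity, neither eye is at 20/200 or below, and this is the participant's first visual event at 70 mg/m². With equal baselines, the better eye at follow-up is the one that lost fewer lines.

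**Rules.** Let L1 and L2 be the lines lost in each eye, and let g be the Table 6-3 grade for a given loss.

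- Cells: grade = g(max(L1, L2)).
- Note: grade = g(min(L1, L2)).

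| More-changed eye | Other eye | Action by the cells | Action by the note | Same? |
|---|---|---|---|---|
| 0-1 | 0-1 | maintain | maintain | yes |
| 2-3 | 0-1 | omit, resume at current dose | maintain | no |
| 2-3 | 2-3 | omit, resume at current dose | omit, resume at current dose | yes |
| 4 or more | 0-1 | omit, reduce to 54 | maintain | no |
| 4 or more | 2-3 | omit, reduce to 54 | omit, resume at current dose | no |
| 4 or more | 4 or more | omit, reduce to 54 | omit, reduce to 54 | yes |

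The action differs in 3 of the 6 band pairs, which are all the pairs with the eyes in different bands. The same count in single lines, 0 to 5 per eye, has 6 × 6 = 36 ordered pairs. Each band holds two values, so 3 × 2 × 2 = 12 pairs agree and 36 − 12 = 24 differ. These are enumerations of possibilities, not probabilities.

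**Size of the dose step.** (70 − 54) / 70 = 16 / 70 = 22.9%. The length of an omission is not fixed, because Table 6-1 ties it to recovery.

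**Carry-over.** The grade also decides when dosing restarts and whether a later event counts as a recurrence. In the 2-3 and 0-1 case, the cells record a first grade 2 event, so a second one leads to reduction. The note records no grade 2 event.

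**Backstop.** Examinations prompted by symptoms also carry a CTCAE symptom grade, which may catch some of these cases. The cycle 3 day 1 examination is scheduled "if no visual symptom(s) are reported, and at study discontinuation". An unequal acuity loss found on cycle 3 day 1 in such a participant has no symptom grade beside it.

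**The case against.** The strongest reply is that one reading gives every word effect. Grades 1 to 3 measure a change and name the eye. Grade 4 alone is an absolute acuity level with no eye named, and a sentence about acuity scores in the better eye fits that cell. Applying it to every grade would empty the either-eye wording in three cells. Table 6-1 points the same way: it is organised by worst toxicity, and its footnote bases dose changes on the most severe preceding toxicity. An investigator with unequal eyes is thus steered to the higher grade.

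That makes the intent likely. It does not settle the text. The note is not limited to grade 4, and the companion sentence on eyeglasses covers all grades. The Table 6-1 footnote says which toxicity governs once graded, not which eye produces the grade.

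It can also be said that the route to harm is narrow. CTCAE grading backs up symptomatic cases, Section 5.3 allows treatment to stop for an abnormal test result, and Section 6.3.3 describes visual symptoms as reversible. All of this lowers the practical risk. None of it removes the gap for a participant without reported symptoms at cycle 3 day 1, and the Section 5.3 route does not say how an unequal acuity loss should be graded.

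**Conclusion.** The point holds as an internal inconsistency in a safety-grading table. Under the assumptions above, the two printed rules give different Table 6-1 actions whenever the eyes fall in different loss bands. The differences run from omit-and-resume versus maintain, up to omit-and-reduce by 22.9% versus maintain. With unequal baselines the rules need not part in the same way: if the better-seeing eye is the one that lost more, both rules pick it.

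A reader might infer that many participants would be misgraded, because Section 2.3.3.2 reports visual adverse events in 71% of patients. Equally, a reader might infer that the extreme case must be very rare, because grade 3/4 events were all below 10% in that study. The documents support neither inference. Those are adverse event rates, not acuity changes by eye, and nothing is given on how closely the two eyes move together. Any modelled frequency would depend on that assumed correlation, so none is claimed.

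Nor does the point reach the efficacy conclusion. The Section 13.1 decision rule counts RECIST responses and does not use the acuity grade, and Section 13.3 treats secondary endpoints as exploratory. This is a minor correction, but one that should be made because the grade drives dosing.

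**What to change.** Make two wording edits to Table 6-3:

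1. For grades 1 to 3, add: *each eye is compared with its own baseline, and the worse-changed eye sets the grade*.
2. Replace the second sentence of the note with: *For grade 4, the acuity level pertains to the better eye*.

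Leave the best-eyeglasses sentence as it is. This writes down the probable intent and agrees with the worst-toxicity principle in Table 6-1. It requires no new test, visit or analysis.
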